Table 11.3.1.1 Continuous Solicited AE by study vaccination number (2-23 months)	123

1. Demographic and baseline values, medication characteristics, specific characteristics

- Baseline characteristics will be reported on the safety set and safety per protocol set.

1.1 Safety Set

Table 1.1.1 Total subject

Safety Set	Total No. subjects (%)
Total	

Table 1.1.2 Demographic characteristics

1) (Administration start date)-(birth)+1

Safety Set		Total No. subjects (%)
Age(years) ¹⁾	No. subjects mean±std median min~max	
Age(months, years)	2-23 months	
	2-10 years	
	2-5 years	
	6-10 years	
	11-18 years	
	19-34 years	
	35-55 years	
	> 55 years	
	Total	
Children group(years)	< 18	
	≥ 18	
	Total	
Ethnic Origin	Asian	
	Black	

Safety Set		Total No. subjects (%)
	Caucasian Hispanic Other	
	Total	
Gender	Male Female	
	Total	
Weight(kg)	No. subjects mean±std median min~max	
Height(cm)	No. subjects mean±std median min~max	

Table 1.1.3 Past diagnosis

Safety Set	Total No. subjects (%)
Yes	
No	
Total	

Table 1.1.4 Pre-Immunization temperature

Safety Set	Total No. subjects (%)
No. subjects mean±std (°C) median min~max	

Table 1.1.5 Temperature Location

Safety Set	Total No. subjects (%)
Axillary	
Oral	
Rectal	
Ear	
Total	

Table 1.1.6 Administration Site

Safety Set	Total No. subjects (%)
Left Deltoid	
Right Deltoid	
Left Thigh (Infant only)	
Right Thigh (Infant only)	
Other	
Total	

Table 1.1.7 Concomitant medication

Safety Set	Total No. subjects (%)
Yes	
No	
Total	

Table 1.1.8 Kidney Disorder

Safety Set	Total No. subjects (%)
Yes	

No	
Total	

Table 1.1.9 Liver disorder

Safety Set	Total No. subjects (%)
Yes	
No	
Total	

Table 1.1.10 Pregnancy

Safety Set	Total No. subjects (%)
Yes	
No	
Total	

Table 1.1.11 Number of previous MenACWY

Safety Set	Total No. subjects (%)
0	
1	
2	
3	
Total	

Table 1.1.12 Study vaccination number

Safety Set	Total No. subjects (%)
1	
2	
3	
4	

Total	
-------	--

1.2 Safety Per Protocol Set

Table 1.2.1 Total subject

Safety per protocol set	Total No. subjects (%)
Total	

Table 1.2.2 Demographic characteristics

1) (Administration start date)-(birth)+1

Safety per protocol set		Total No. subjects (%)
Age(years) ¹⁾	No. subjects mean±std median min~max	
Age(months, years)	2-23 months	
	2-10 years	
	2-5 years	
	6-10 years	
	11-18 years	
	19-34 years	
	35-55 years	
	Total	
Children group(years)	< 18	
	≥ 18	
	Total	
Ethnic Origin	Asian	
	Black	
	Caucasian	
	Hispanic	
	Other	
	Total	
Gender	Male	

Safety per protocol set		Total No. subjects (%)
	Female	
	Total	
Weight(kg)	No. subjects mean±std median min~max	
Height(cm)	No. subjects mean±std median min~max	

Table 1.2.3 Past diagnosis

Safety per protocol set	Total No. subjects (%)
Yes	
No	
Total	

Table 1.2.4 Pre-Immunization temperature

Safety per protocol set	Total No. subjects (%)
No. subjects	
mean±std (°C)	
median	
min~max	

Table 1.2.5 Temperature Location

Safety per protocol set	Total No. subjects (%)
Axillary	
Oral	
Rectal	
Ear	
Total	

Table 1.2.6 Administration Site

Safety per protocol set	Total No. subjects (%)
Left Deltoid	
Right Deltoid	
Left Thigh (Infant only)	
Right Thigh (Infant only)	
Other	
Total	

Table 1.2.7 Concomitant medication

Safety per protocol set	Total No. subjects (%)
Yes	
No	
Total	

Table 1.2.8 Kidney Disorder

Safety per protocol set	Total No. subjects (%)
Yes	
No	
Total	

Table 1.2.9 Liver disorder

Safety per protocol set	Total No. subjects (%)
Yes	
No	
Total	

Table 1.2.10 Pregnancy

Safety per protocol set	Total No. subjects (%)
Yes	
No	
Total	

Table 1.2.11 Number of previous MenACWY

Safety per protocol Set	Total No. subjects (%)
0	
1	
2	
3	
Total	

Table 1.2.12 Study vaccination number

Safety per protocol Set	Total No. subjects (%)
1	
2	
3	
4	
Total	

2. Safety Analyses

- AE includes solicited and unsolicited AE (Day 1-7) and medically attended AE (Day 1-29) and SAEs (Day 1-29)
- AE will be reported on the safety set and safety per protocol set.
- SAE/SADR will be reported on the safety set, safety per protocol set and non-safety per protocol set.

2.1 Safety Set

Table 2.1.1 Summary of AE

Safety set	No. subjects with AE n (%)	95% CI† for the percentage of subjects with AE (Lower , Upper)	No. AEs n	No. subjects with ADR n (%)	95% CI† for t percentage o subjects with A (Lower , Upp
Solicited AE (2-23 months)					
Local AE					
Systemic AE					
Solicited AE (2-5 years)					
Local AE					
Systemic AE					
Solicited AE (≥ 6 years)					
Local AE					
Systemic AE					

Safety set	No. subjects with AE n (%)	95% CI† for the percentage of subjects with AE (Lower ,Upper)	No. AEs n	No. subjects with ADR n (%)	95% CI† for the percentage of subjects with ADR (Lower ,Upper)	No. ADR n	Total n (%)
Unsolicited AE							
SAE							
MAAE							
Death							
Total							

† 95% CI will be calculated using the normal approximation.

* Day 1-7: Solicited AE, Unsolicited AE

* Day 1-29: SAE, Death

* Day 8-29: MAAE

Table 2.1.2 Summary of AE by Age (month, year)

Safety Set	No. subjects with AE	No. AEs	Total	p-value
	n (%)	n	n (%)	
2-23 months				X ² -test or Exact test
2-10				
2-5				
6-10				
11-18				
19-34				
35-55				
> 55				
Total				

Table 2.1.3 Summary of AE by Age (month, year)

Safety Set	No. subjects with AE	No. AEs	Total	p-value
	n (%)	n	n (%)	
Solicited AE				X ² -test or Exact test
2-23 months				
2-10				
2-5				
6-10				
11-18				
19-34				
35-55				
> 55				
Solicited Local AE				X ² -test or Exact test
2-23 months				
2-10				
2-5				
6-10				
11-18				
19-34				

Safety Set	No. subjects with AE n (%)	No. AEs n	Total n (%)	p-value
35-55 > 55				
Solicited Systemic AE 2-23 months 2-10 2-5 6-10 11-18 19-34 35-55 ≥56				X ² -test or Exact test
Unsolicited AE 2-23 months 2-10 2-5 6-10 11-18 19-34 35-55 ≥56				X ² -test or Exact test
SAE 2-23 months 2-10 2-5 6-10 11-18 19-34 35-55 ≥56				X ² -test or Exact test
MAAE 2-23 months 2-10 2-5				X ² -test or Exact test

Safety Set	No. subjects with AE n (%)	No. AEs n	Total n (%)	p-value
6-10				
11-18				
19-34				
35-55				
≥56				
ADR				
2-23 months				
2-10				
2-5				
6-10				X ² -test or Exact test
11-18				
19-34				
35-55				
≥56				
Death				
2-23 months				
2-10				
2-5				
6-10				X ² -test or Exact test
11-18				
19-34				
35-55				
≥56				

Table 2.1.4 Summary of AE by Children group

Safety Set	No. subjects with AE n (%)	No. AEs n	Total n (%)	p-value
< 18 years				
≥ 18 years				X ² -test or Exact test
Total				

Table 2.1.5 Summary of AE by Gender

Safety Set	No. subjects with AE n (%)	No. AEs n	Total n (%)	p-value
Male				X ² -test or Exact test
Female				
Total				

Table 2.1.6 Summary of AE by Past diagnosis

Safety Set	No. subjects with AE n (%)	No. AEs n	Total n (%)	p-value
Yes				X ² -test or Exact test
No				
Total				

Table 2.1.7 Summary of AE by Temperature Location

Safety Set	No. subjects with AE n (%)	No. AEs n	Total n (%)	p-value
Axillary				X ² -test or Exact test
Oral				
Rectal				
Ear				
Total				

Table 2.1.8 Summary of AE by Administration Site

Safety Set	No. subjects with AE n (%)	No. AEs n	Total n (%)	p-value
Left Deltoid				X ² -test or Exact test
Right Deltoid				
Left Thigh (Infant only)				
Right Thigh (Infant only)				
Other				
Total				

Table 2.1.9 Summary of AE by Concomitant medication

Safety Set	No. subjects with AE n (%)	No. AEs n	Total n (%)	p-value
Yes				X ² -test or Exact test
No				
Total				

Table 2.1.10 Summary of AE by Kidney Disorder

Safety Set	No. subjects with AE n (%)	No. AEs n	Total n (%)	p-value
Yes				X ² -test or Exact test
No				
Total				

Table 2.1.11 Summary of AE by Liver disorder

Safety Set	No. subjects with AE n (%)	No. AEs n	Total n (%)	p-value
Yes				X ² -test or Exact test
No				
Total				

Table 2.1.12 Summary of AE by Pregnancy

Safety Set	No. subjects with AE n (%)	No. AEs n	Total n (%)	p-value
Yes				X ² -test or Exact test
No				
Total				

Table 2.1.13 Summary of AE by Number of previous MenACWY

Safety Set	No. subjects with AE n (%)	No. AEs n	Total n (%)	p-value
0				X ² -test or Exact test
1				
2				
3				
Total				

Table 2.1.14 Summary of AE by Study vaccination number

Safety Set	No. subjects with AE n (%)	No. AEs n	Total n (%)	p-value
1				

Safety Set	No. subjects with AE n (%)	No. AEs n	Total n (%)	p-value
2				X ² -test or Exact test
3				
4				
Total				

2.2 Safety per protocol set

Table 2.2.1 Summary of AE

Safety per protocol set	No. subjects with AE n (%)	95% CI† for the percentage of subjects with AE (Lower , Upper)	No. AEs n	No. subjects with ADR n (%)	95% CI† for the percentage of subjects with ADR (Lower , Upper)	No. ADR n	Total n (%)
Solicited AE (2-23 months)							
Local AE							
Systemic AE							
Solicited AE (2-5 years)							
Local AE							
Systemic AE							
Solicited AE (≥ 6 years)							
Local AE							
Systemic AE							
Unsolicited AE							
SAE							
MAAE							
Death							
Total							

† 95% CI will be calculated using the normal approximation.

* Day 1-7: Solicited AE, Unsolicited AE

* Day 1-29: SAE, Death

* Day 8-29: MAAE

Table 2.2.2 Summary of AE by Age (month, year)

Safety per protocol Set	No. subjects with AE n (%)	No. AEs n	Total n (%)	p-value
2-23 months				X ² -test or Exact test
2-10				
2-5				
6-10				
11-18				
19-34				
35-55				
Total				

Table 2.2.3 Summary of AE by Age (year)

Safety Set	No. subjects with AE n (%)	No. AEs n	Total n (%)	p-value
Solicited AE				X ² -test or Exact test
2-23 months				
2-10				
2-5				
6-10				
11-18				
19-34				
35-55				
Solicited Local AE				X ² -test or Exact test
2-23 months				
2-10				
2-5				
6-10				
11-18				
19-34				
35-55				
Solicited Systemic AE				

Safety Set	No. subjects with AE n (%)	No. AEs n	Total n (%)	p-value
2-23 months				X ² -test or Exact test
2-10				
2-5				
6-10				
11-18				
19-34				
35-55				
Unsolicited AE				X ² -test or Exact test
2-23 months				
2-10				
2-5				
6-10				
11-18				
19-34				
35-55				
SAE				X ² -test or Exact test
2-23 months				
2-10				
2-5				
6-10				
11-18				
19-34				
35-55				
MAAE				X ² -test or Exact test
2-23 months				
2-10				
2-5				
6-10				
11-18				
19-34				
35-55				
ADR				X ² -test or Exact test
2-23 months				

Safety Set	No. subjects with AE n (%)	No. AEs n	Total n (%)	p-value
2-10				
2-5				
6-10				
11-18				
19-34				
35-55				
Death				X ² -test or Exact test
2-23 months				
2-10				
2-5				
6-10				
11-18				
19-34				
35-55				

Table 2.2.4 Summary of AE by Children group

Safety per protocol Set	No. subjects with AE n (%)	No. AEs n	Total n (%)	p-value
< 18 years				X ² -test or Exact test
≥ 18 years				
Total				

Table 2.2.5 Summary of AE by Gender

Safety per protocol Set	No. subjects with AE n (%)	No. AEs n	Total n (%)	p-value
Male				X ² -test or Exact test
Female				
Total				

Table 2.2.6 Summary of AE by Past diagnosis

Safety per protocol Set	No. subjects with AE n (%)	No. AEs n	Total n (%)	p-value
Yes				X ² -test or Exact test
No				
Total				

Table 2.2.7 Summary of AE by Temperature Location

Safety per protocol Set	No. subjects with AE n (%)	No. AEs n	Total n (%)	p-value
Axillary				X ² -test or Exact test
Oral				
Rectal				
Ear				
Total				

Table 2.2.8 Summary of AE by Administration Site

Safety per protocol Set	No. subjects with AE n (%)	No. AEs n	Total n (%)	p-value
Left Deltoid				X ² -test or Exact test
Right Deltoid				
Left Thigh (Infant only)				
Right Thigh (Infant only)				
Other				
Total				

Table 2.2.9 Summary of AE by Concomitant medication

Safety per protocol Set	No. subjects with AE n (%)	No. AEs n	Total n (%)	p-value
Yes				X ² -test or Exact test
No				
Total				

Table 2.2.10 Summary of AE by Kidney Disorder

Safety per protocol Set	No. subjects with AE n (%)	No. AEs n	Total n (%)	p-value
Yes				X ² -test or Exact test
No				
Total				

Table 2.2.11 Summary of AE by Liver disorder

Safety per protocol Set	No. subjects with AE n (%)	No. AEs n	Total n (%)	p-value
Yes				X ² -test or Exact test
No				
Total				

Table 2.2.12 Summary of AE by Pregnancy

Safety per protocol Set	No. subjects with AE n (%)	No. AEs n	Total n (%)	p-value
Yes				X ² -test or Exact test
No				
Total				

Table 2.2.13 Summary of AE by Number of previous MenACWY

Safety per protocol Set	No. subjects with AE n (%)	No. AEs n	Total n (%)	p-value
0				X ² -test or Exact test
1				
2				
3				
Total				

Table 2.2.14 Summary of AE by Study vaccination number

Safety per protocol Set	No. subjects with AE n (%)	No. AEs n	Total n (%)	p-value
1				X ² -test or Exact test
2				
3				
4				
Total				

3. Information of AEs

3.1 Safety Set

Table 3.1.1 Summary of solicited AE and unsolicited AE for 7 days after vaccination (<6 years)

Safety Set		AE	
		Incidence Rate n (%)	No. of AEs n
Local AE	Local AE		
	Injection site tenderness		
	Injection site erythema		
	Injection site induration		
Systemic AE	Systemic AE		
	Change in eating habits		
	Sleepiness		
	Irritability		
	Vomiting		
	Diarrhea		
	Rash		
	Fever		
UNSOLICITED AE	System Organ Class(SOC)		
	Preferred Term(PT)		
	Sub Total		
Total			

Table 3.1.2 Summary of solicited AE and unsolicited AE for 7 days after vaccination (<6 years)

Safety Set		AE(2-23 months) N=0		AE(2-5years) N=0	
		Incidence Rate n (%)	No. of AEs n	Incidence Rate n (%)	No. of AEs n
Local AE	Local AE				
	Pain				
	Erythema				
	Induration				
Systemic AE	Systemic AE				
	Chills				
	Nausea				
	Malaise				
	Myalgia				
	Arthralgia				
	Headache				
	Rash				
	Fever				
	Sub Total				
UNSOLICITED AE	System Organ Class(SOC)				
	Preferred Term(PT)				
	Sub Total				
Total					

Table 3.1.3 Summary of solicited AE and unsolicited AE for 7 days after vaccination by study vaccination number (2-23months)

Safety Set		1 N=0		2 N=0		3 N=0		4 N=0	
		Incidence Rate	No. of AEs						
		n (%)	n						
Local AE	Local AE								
	Pain								
	Erythema Induration								
Systemic AE	Systemic AE								
	Chills								
	Nausea								
	Malaise								
	Myalgia								
	Arthralgia								
	Headache								
	Rash								
	Fever								
	Sub Total								
UNSOLICITED AE	System Organ Class(SOC)								
	Preferred Term(PT)								

Table 3.1.4 Summary of solicited AE and unsolicited AE for 7 days after vaccination (\geq 6years)

Safety Set		AE	
		Incidence Rate n (%)	No. of AEs n
Local AE	Local AE		
	Pain		
	Erythema		
	Induration		
Systemic AE	Systemic AE		
	Chills		
	Nausea		
	Malaise		
	Myalgia		
	Arthralgia		
	Headache		
	Rash		
	Fever		
UNSOLICITED AE	System Organ Class(SOC)		
	Preferred Term(PT)		
	Sub Total		
Total			

Table 3.1.5 Summary of solicited AE and unsolicited AE for 7 days after vaccination (≥ 6 years)

Safety Set		AE(6-10)		AE(11-18)		AE(19-34)		AE(35-55)		AE(≥ 56)	
		N=0		N=0		N=0		N=0		N=0	
		Incidence Rate (n %)	No of AEs (n)								
Local AE	Local AE										
	Pain Erythema Induration										
Systemic AE	Systemic AE										
	Chills Nausea Malaise Myalgia Arthralgia Headache Rash Fever										
	Sub Total										
UNSOLICITED AE	System Class(SOC)										
	Organ Preferred Term(PT)										
	Sub Total										
Total											

Table 3.1.6 Summary of medically attended AEs for 8 days to 28 days after vaccination

Safety Set		AE	
		Incidence Rate n (%)	No. of AEs n
MAAE	System Organ Class(SOC)		
	Preferred Term(PT)		
Total			

Table 3.1.7 Summary of medically attended AEs for 8 days to 28 days after vaccination

Safety Set		AE(2-23months) N=0		AE(2-10) N=0		AE(11-18) N=0		AE(19-34) N=0		AE(35-55) N=0		AE(≥56) N=0	
		Incidence Rate	No. of AEs	Incidence Rate	No. of AEs	Incidence Rate	No. of AEs	Incidence Rate	No. of AEs	Incidence Rate	No. of AEs	Incidence Rate	No. of AEs
		n (%)	n	n (%)	n	n (%)	n	n (%)	n	n (%)	n	n (%)	n
MAAE	System Organ Class(SOC)												
	Preferred Term(PT)												
Total													

Table 3.1.8 Summary of medically attended AEs for 8 days to 28 days after vaccination by study vaccination number (2-23 months)

Safety Set		1 N=0		2 N=0		3 N=0		4 N=0	
		Incidence Rate	No. of AEs						
		n (%)	n						
MAAE	System Organ Class(SOC)								
	Preferred Term(PT)								
Total									

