In case the Diary Card is not retrieved within 10 days after Day 29, subject or subject’s parent/legal representative will be contacted by phone to assess the occurrence of adverse events, determine the subject’s clinical status and complete study termination. All information will be recorded by the site staff on the subject’s medical record and collected in the appropriate section of the CRF.

All SAEs will be monitored until resolution and/or the cause is identified. If a SAE remains unresolved at study termination, a clinical assessment will be made by the investigator and the GSK regional physician to determine whether continued follow up of the SAE is needed.

Table 3.1-1: Safety Assessment Table

Medical History: All significant past diagnoses including all allergies, major surgeries requiring inpatient hospitalization, other significant injuries or hospitalizations, any conditions requiring prescription or chronic medication (i.e., >2 weeks in duration), or other significant medical conditions based on the investigator’s judgment.
	
From birth, collected at clinic visit Day 1

---	--

	CONFIDENTIAL :	Last Update Date
	THIS DOCUMENT AND INFORMATION CONTAINED HEREIN IS PROPRIETARY TO COMPANY AND IS NOT TO BE DISCLOSED WITHOUT THE WRITTEN PERMISSION OF COMPANY.	26-JAN-2016
STATISTICAL ANALYSIS PLAN(V4.0)		

Immediate reactions: Subjects will be assessed for immediate hypersensitivity reactions.	For at least 30 minutes after vaccination
Solicited local adverse events: < 6 years : injection site erythema, injection site induration, injection site tenderness ≥ 6 years : injection site erythema, injection site induration, injection site pain	Days 1-7 after vaccination
Solicited systemic adverse events: < 6 years : change in eating habits, sleepiness, irritability, rash, vomiting, diarrhea, fever ≥ 6 years : chills, nausea, malaise, generalized myalgia, generalized arthralgia, headache, rash, fever	Days 1-7 after vaccination
All unsolicited AEs will be collected	Days 1-7 after vaccination
Medically attended Adverse Events: Events that require a physician's visit or an emergency room visit (events that are managed by telephone or means other than a face-to-face evaluation by a clinician do not qualify as medically attended AEs).	From Day 1 to study termination (Day 29/early termination)
Serious AEs: All SAEs will be collected.	From Day 1 to study termination (Day 29/early termination)

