3.2 Safety per protocol set

Table 3.2.1 Summary of solicited AE and unsolicited AE for 7 days after vaccination (<6 years)

Safety per protocol Set		AE	
		Incidence Rate n (%)	No. of AEs n
Local AE	Local AE		
	Injection site tenderness		
	Injection site erythema		
	Injection site induration		
Systemic AE	Systemic AE		
	Change in eating habits		
	Sleepiness		
	Irritability		
	Vomiting		
	Diarrhea		
	Rash		
	Fever		
UNSOLICITED AE	System Organ Class(SOC)		
	Preferred Term(PT)		
	Sub Total		
Total			

Table 3.2.2 Summary of solicited AE and unsolicited AE for 7 days after vaccination (<6 years)

Safety per protocol Set		AE(2-23 months) N=0		AE(2-5years) N=0	
		Incidence Rate n (%)	No. of AEs n	Incidence Rate n (%)	No. of AEs n
Local AE	Local AE				
	Pain				
	Erythema Induration				
Systemic AE	Systemic AE				
	Chills				
	Nausea				
	Malaise				
	Myalgia				
	Arthralgia				
	Headache				
	Rash Fever				
	Sub Total				
UNSOLICITED AE	System Organ Class(SOC)				
	Preferred Term(PT)				
	Sub Total				
Total					

Table 3.2.3 Summary of solicited AE and unsolicited AE for 7 days after vaccination by study vaccination number (2-23months)

Safety per protocol Set		1 N=0		2 N=0		3 N=0		4 N=0	
		Incidence Rate	No. of AEs						
		n (%)	n						
Local AE	Local AE								
	Pain								
	Erythema Induration								
Systemic AE	Systemic AE								
	Chills								
	Nausea								
	Malaise								
	Myalgia								
	Arthralgia								
	Headache								
	Rash								
	Fever								
	Sub Total								
UNSOLICITED AE	System Organ Class(SOC)								
	Preferred Term(PT)								

Safety per protocol Set		1 N=0		2 N=0		3 N=0		4 N=0	
		Incidence Rate	No. of AEs						
		n (%)	n						
	Sub Total								
Total									

Table 3.2.4 Summary of solicited AE and unsolicited AE for 7 days after vaccination (≥ 6 years)

Safety per protocol Set		AE	
		Incidence Rate n (%)	No. of AEs n
Local AE	Local AE		
	Pain		
	Erythema		
	Induration		
Systemic AE	Systemic AE		
	Chills		
	Nausea		
	Malaise		
	Myalgia		
	Arthralgia		
	Headache		
	Fever		
UNSOLICITED AE	System Organ Class(SOC)		
	Preferred Term(PT)		
	Sub Total		
Total			

Table 3.2.5 Summary of solicited AE and unsolicited AE for 7 days after vaccination (≥ 6 years)

Safety per protocol Set		AE(6-10) N=0		AE(11-18) N=0		AE(19-34) N=0		AE(35-55) N=0	
		Incidence Rate	No. of AEs						
		n (%)	n						
Local AE	Local AE								
	Pain								
	Erythema Induration								
Systemic AE	Systemic AE								
	Chills								
	Nausea								

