DATE OF REVISION	INDICATION REVISION	REASON FOR CHANGE	AUTHOR NAME
22-NOV-2013	All	Protocol Amendment	PPD
10-APR-2014	Appendix1	Modification of tables to include incidence rate of ADR, Fever added to Solicited reaction	PPD
26-JAN-2016	All	Protocol Amendment	PPD
07-JUL-2016	6.3 Additional Analyses for DDS (Data Disclosure Shell)	Add the DDS(Data Disclosure Shell) analysis	PPD
	7.4 Additional Analyses for DDS (Data Disclosure Shell)	Add the DDS(Data Disclosure Shell) analysis	
	8. Notes	Add the DDS(Data Disclosure Shell) analysis in re-examination report	
	Appendix1	Add the DDS(Data Disclosure Shell) analysis	
20-APR-2018	All	Using more appropriate word	PPD
	6.2.3 Analysis of Unsolicited AE	Change the of criteria MAAE	

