In case the Diary Card is not retrieved within 10 days after Day 29, subject or subject’s parent/legal representative will be contacted by phone to assess the occurrence of adverse events, determine the subject’s clinical status and complete study termination. All information will be recorded by the site staff on the subject’s medical record and collected in the appropriate section of the CRF.

All SAEs will be monitored until resolution and/or the cause is identified. If a SAE remains unresolved at study termination, a clinical assessment will be made by the investigator and the GSK regional physician to determine whether continued follow up of the SAE is needed.

Table 3.1-1: Safety Assessment Table

Medical History: All significant past diagnoses including all allergies, major surgeries requiring inpatient hospitalization, other significant injuries or hospitalizations, any conditions requiring prescription or chronic medication (i.e., >2 weeks in duration), or other significant medical conditions based on the investigator’s judgment.
	
From birth, collected at clinic visit Day 1

---	--

	CONFIDENTIAL :	Last Update Date
	THIS DOCUMENT AND INFORMATION CONTAINED HEREIN IS PROPRIETARY TO COMPANY AND IS NOT TO BE DISCLOSED WITHOUT THE WRITTEN PERMISSION OF COMPANY.	20-APR-2018
STATISTICAL ANALYSIS PLAN(V6.0)		

Immediate reactions: Subjects will be assessed for immediate hypersensitivity reactions.
	For at least 30 minutes after vaccination

Solicited local adverse events: < 6 years : injection site erythema, injection site induration, injection site tenderness ≥ 6 years : injection site erythema, injection site induration, injection site pain
	Days 1-7 after vaccination

Solicited systemic adverse events: < 6 years : change in eating habits, sleepiness, irritability, rash, vomiting, diarrhea, fever ≥ 6 years : chills, nausea, malaise, generalized myalgia, generalized arthralgia, headache, rash, fever
	Days 1-7 after vaccination
All unsolicited AEs will be collected	Days 1-7 after vaccination

Medically attended Adverse Events: Events that require a physician's visit or an emergency room visit (events that are managed by telephone or means other than a face-to-face evaluation by a clinician do not qualify as medically attended AEs).
	From Day 1 to study termination (Day 29/early termination)

Serious AEs: All SAEs will be collected.
	From Day 1 to study termination (Day 29/early termination)

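### In SAP V4.0 Appendix 1, four under-6 symptom shells, including the only Day 1–7 infant ones by dose number, list the symptoms solicited at 6 years and over

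*SAP*

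**What the plan says.** The Safety Assessment Table in Section 2.4 of SAP V4.0 fixes what is solicited on Days 1–7, with a split at 6 years.

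- Under 6, local: "< 6 years : injection site erythema, injection site induration, injection site tenderness".
- Under 6, systemic: "< 6 years : change in eating habits, sleepiness, irritability, rash, vomiting, diarrhea, fever".
- From 6 years, local: "≥ 6 years : injection site erythema, injection site induration, injection site pain". The systemic list for this group is chills, nausea, malaise, myalgia, arthralgia, headache, rash and fever.

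Section 2.4 of V6.0 keeps the under-6 systemic list unchanged ("change in eating habits, sleepiness, irritability, rash, vomiting, diarrhea, fever"), and Section 6.2.2 in both versions defines severity grades for the under-6 symptoms.

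In V4.0 Appendix 1, Tables 3.1.1 and 3.2.1 pool all children under 6 and carry the under-6 list. The next tables do not. "Table 3.1.2 Summary of solicited AE and unsolicited AE for 7 days after vaccination (<6 years" has columns for 2–23 months and 2–5 years. "Table 3.1.3 Summary of solicited AE and unsolicited AE for 7 days after vaccination by study vaccination number (2-23months" has columns for study vaccinations 1 to 4 in infants. Table 3.2.2 and "Table 3.2.3 Summary of solicited AE and unsolicited AE for 7 days after vaccination by study vaccination number (2-23months" repeat the pair for the per-protocol set. All four list pain, erythema and induration as local events, and chills through headache plus rash and fever as systemic events.

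After V4.0, the only revision-log entry naming Appendix 1 is "Add the DDS(Data Disclosure Shell) analysis", made for V5.0. The V6.0 entries are a general rewording of the document, a change to the criteria for medically attended events, and an added product-label analysis.

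**The concern.** A shell tells the programmer which rows to fill. Here most rows name symptoms that nobody was asked about in this age group, and most symptoms that were asked about have nowhere to go. An empty or zero row for headache or myalgia in infants could be read as an observed absence, when the symptom was never solicited. The any-local and any-systemic rows in the same tables would also be ambiguous: built from the listed rows they would understate reactions, and built from the collected symptoms they would not match the rows beneath them.

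The by-dose tables matter most. Protocol Amendment 2 added infants to meet a regulator's requirement, and Amendment 3 allowed follow-up after later doses in the infant series. Reactogenicity by dose is the main new information that this follow-up can yield.

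**Working it through.** There is no sample size or power figure to reproduce. The check is a comparison of row labels with the two solicited lists, treating generalized myalgia and arthralgia as the rows labelled myalgia and arthralgia.

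**Lists (Section 2.4)**

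- Solicited under 6: 3 local + 7 systemic = 10.
- Solicited from 6 years: 3 local + 8 systemic = 11.
- Rows in Tables 3.1.2, 3.1.3, 3.2.2 and 3.2.3: 3 local + 8 systemic = 11.

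**Comparison**

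| Group | Symptoms | Count |
|---|---|---|
| In the shells and solicited under 6 | erythema, induration, rash, fever | 4 |
| In the shells, not solicited under 6 | pain, chills, nausea, malaise, myalgia, arthralgia, headache | 11 − 4 = 7 |
| Solicited under 6, no row | tenderness, changed eating, sleepiness, irritability, vomiting, diarrhea | 10 − 4 = 6 |

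The 11 rows are exactly the list for 6 years and over. So 7 of 11 rows do not belong, and 6 of 10 collected symptoms are missing.

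**How far the error extends in V4.0 Appendix 1**

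Nine symptom-level shells per analysis set cover children under 6: 3.1.1, 3.1.2, 3.1.3, 4.1.1, 4.1.3, 4.1.4, 4.1.6, 4.1.7 and 4.1.9, with their 3.2 and 4.2 counterparts. That makes 2 × 9 = 18. Four are wrong and 18 − 4 = 14 carry the right symptoms.

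**What can replace the four**

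- By age group: Tables 4.1.3, 4.1.6 and 4.1.9, and 4.2.3, 4.2.6 and 4.2.9, have separate blocks for 2–23 months and 2–5 years with the under-6 symptoms and a total column. All six missing symptoms appear there.
- By dose number: Table 2.1.14 gives adverse events overall, without symptoms. Tables 11.1.1.1, 11.2.1.1 and 11.3.1.1 cover only continuous solicited events, coded by organ class and preferred term. Section 6.2.3 (V4.0 and V6.0) asks for results by vaccination number for serious, unexpected, medically attended, unsolicited and continuous solicited events, but not for Day 1–7 solicited symptoms. Nothing else supplies what Tables 3.1.3 and 3.2.3 were meant to show.

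**The case against.** Three arguments on the other side have weight.

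**The infant symptom profile is specified elsewhere.** This stands. A reader might infer from the four tables that infant reactions would largely go unreported, or that these are the only shells separating infants from 2–5-year-olds. The Section 4 shells contradict both readings, in both analysis sets. The substitution is not quite complete: Table 3.1.2 also counts events, and the severity tables include an absent size class (0–9 mm) and a no-rash category among their graded columns. Neither limit affects the six missing symptoms.

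**V4.0 was superseded.** This stands in part. The V5.0 and V6.0 appendices are not in the documents, so a reader cannot conclude that the final tables had these rows. Silence in the log is weak evidence. V6.0 added a 55–64 age group and changed the disclosure age bands without itemising either change. V4.0 corrected the under-6 size cut-offs in Table 4.1.1 under a general entry. The V4.0 shells also put medically attended events on Days 8–29, while V6.0 Section 6.2.3 uses Days 1–29. V6.0's cross-reference to Appendix 1 does not help either way, because it names only Tables 4.1.3 and 4.2.3, whose rows are right. Still, no correction of the four tables is recorded.

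**The SAP text is correct, so this is clerical.** Agreed on the likely cause: the correct neighbouring tables suggest a copied template, and no endpoint definition is affected. But for Day 1–7 symptoms by dose the text asks for nothing that would override the shell, so there the shell is the specification.

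**Conclusion.** The point holds for the four named V4.0 shells and is minor. It is an internal inconsistency between the solicited lists and the tables meant to report them: 7 of 11 rows are wrong and 6 of 10 collected symptoms are absent, in 4 of 18 under-6 symptom shells. The real loss is confined to Tables 3.1.3 and 3.2.3, where the infant Day 1–7 symptom profile by study vaccination number has no correct shell anywhere. The age-group results are duplicated correctly in Section 4 of the appendix.

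The cohort concerned is planned at 600 evaluable infants (Section 2.2). That is the size of the cohort, not a count of infants whose reactions would be lost, and the documents do not say how many would be followed for more than one dose.

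The conclusion assumes that the shells would be programmed as written and that the V4.0 rows carried forward. The second assumption can be neither confirmed nor excluded from the documents.

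**What to change.** Replace the symptom rows in Tables 3.1.2, 3.1.3, 3.2.2 and 3.2.3 with those already in Tables 3.1.1 and 3.2.1: tenderness, erythema and induration as local events; changed eating, sleepiness, irritability, vomiting, diarrhea, rash and fever as systemic events. Derive the any-local and any-systemic rows from the same list. If the final Appendix 1 already has these rows, it is enough to say so and to record the correction in the revision log. The cost is an edit to four shells and their programs. The symptoms are already collected, so no new data are needed.
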